5.4 Consent

DoxyMe

We will telephone potential candidates for this study who are identified in the ACT database. A telephone script will identify the research coordinator and establish a time convenient for DoxyMe consent to begin.

Consent will review in detail the nature of the Alpha-1 Carrier Genomics Study, as well as potential risks and benefits of participation and the option to not participate.

Informed consent and signature of HIPAA will take place via DoxyMe, a free and HIPAA compliant telemedicine service. While the consenting research personnel and the potential participant are connected by video and voice on the DoxyMe server, the informed consent will be electronically sent to the participant via this platform for real time signature and return. The participant will have the informed consent and HIPPA form reviewed by the trained study coordinator. Adequate time will be given for each potential enrollee to read, understand and ask questions about the research study. Once the consent form is signed, dated and electronically returned via DoxyMe, the consenting coordinator will sign and date it, as well. At this point the participant is enrolled. The completed forms are then submitted to and stored in the electronic database established for the study. Participants will be encouraged to retain their copy for their records. Note that there is no paper copy of this consent form.

If necessary, paper consents may be mailed, with the consenting process taking place by telephone. In this event, following adequate opportunity to ask questions willing participants will sign the consent and HIPAA forms and return them to the consenting member of the research team by fax or mail. At the same time, the consenting member of the research team will also sign and date a copy of both the consent and HIPAA forms. Once the participant's signed forms are received, they will be stapled together with those signed by the consenting team member and a note entered at the bottom of the patient's consent linking the files. At this point the participant is enrolled. The complete paperwork is then scanned as a pdf and submitted to the electronic database established for the study. Participants will be encouraged to retain their copy for their records.

All pages of any paper consents will be digitized, reviewed by a team member to confirm that all pages are present and legible, facing the appropriate direction and are an exact copy of the paper consent. Each consent will be individually labeled with the participant's study ID. The consents will be saved in a secure server and indexed for immediate access by authorized study team members. Certification that the pdf consent is identical to the paper copy will be added as initials and date in adobe acrobat. After certification has been added the file will be locked and saved. The original paper consents will be kept in a locked file cabinet in the Alpha-1 office.

5.5 Withdrawal

A participant may withdraw from the study at any time for any reason. At the time of withdrawal the participant may 1) decline to provide any more data or specimens to the study but allow use of previously collected data and/or specimens, 2) request withdrawal of all his/her data from study databases and request that any stored samples be destroyed, or 3) withdraw some portion of the data collected (i.e. participants may withdraw specimens but not questionnaire data or vice versa). Genomic sequencing results in extensive genetic data, including genetic sequence that cannot be unknown. Laboratories often retain records of all sequence data that results from testing in their facility. Participants may not be able to recover all records of their genomic sequence; however, the laboratory sequence data will be linked only to study number in their records and no personally identifying information will be linked. Participants may specify that they wish for data that results from sequencing of their assigned study number to be omitted from research analysis or use; however, such data may not cease to exist upon withdrawal.

If a participant chooses to withdraw the research coordinator will determine the disposition of the participant's study data and provide the participant with any clinically relevant study results, or establish how the participant would like to be contacted if relevant results become available in the future.

5.6. Study Schedule

1. Following IRB approval and establishment of CSL contracts study coordinators will contact lower quartile MZ individuals by telephone to invite them to participate and schedule informed consent. Follow-up calls may be made to boost initial recruitment and matching.

- 2. For each informed consent and questionnaire set received, a barcoded DNA1 test kit will be mailed with instructions for obtaining and returning the required sample. Postage paid return mailing supplies will be provided.
- 3. The samples returned will go by US Postal Service directly to the Biocerna lab for testing. Biocerna will have the sample and barcode only (no personal health information), while all survey items and identifiers are collected and stored for linkage at MUSC.
- 4. MUSC will perform matching of age, sex, and smoking-status COPD-affected and control MZ participants.
- 5. Biocerna LLC will perform *SERPINA1* sequencing on samples sent by participants and provide laboratory interpretation of likely pathogenicity to study personnel.
- 6. Study personnel will link the results to the participant and mail results to the participant. The results will include a study interpretation of results and recommendations for accessing appropriate resources.

7.

- 8. Statistical analysis of all matched pairs using paired T-test and descriptive analysis will allow for conclusions of this pilot study to be made. Participants for whom no match is available in the study cohort will be included in an uneven COPD+ / arm analysis and aggregate study reporting.
- 9. The study will be complete in approximately 2 years, with subsequent publication of results, including an abstract for the American Thoracic Society annual meeting in May 2016.

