Genetic variation in the Alpha-1 gene has been incompletely studied. While historical texts suggest ~100 different SERPINA1 alleles, modern genetic databases remain largely proprietary to each lab but > 500 AAT alleles are now estimated. This biases against publication of new variants. Of some interest is the ability to sequence upstream and downstream from the coding sequence of *SERPINA1* which has allowed detection of significant deletions of major portions of the gene. With this background we hypothesize that *SERPINA1* gene sequencing performed through the DNA1 testing platform will find important sequence variations in individuals who have COPD compared to age, race, sex, AAT level and smoking status matched individuals who do not have COPD in the PiMZ ACT cohort.

The Alpha Coded Testing (ACT) Study is an established and confidential home genetic testing study for alpha-1 antitrypsin deficiency (AATD). Two primary populations choose to test through ACT. This is a preferred program for individuals in the US to test family members of those who have been found severely deficient. In addition, this test is used by individuals with COPD who choose to test in a confidential manner. The ACT Study is sponsored and endorsed by the Alpha-1 Foundation. As a result of the demographics, 27% of the ACT cohort adults who complete testing are found to have one Z allele (N=4153). The serum levels estimated from these blood spot cards are non-normally distributed with significant variation.

ACT participants with heterozygous genotype MZ will be invited to participate in this matched-control study. In the absence of spirometry in ACT, the validated COPD severity score³ has been used to define

the presence and grade the severity of COPD from questionnaires. The primary outcome of this study will capture the number and features of *SERPINA1* variants between the two groups and allow correlation to COPD presence and severity.

Specific Aims

- 1.1 To identify rare *SERPINA1* sequence variants that correlate with presence and severity of COPD in MZ carriers of Alpha-1 antitrypsin deficiency.
- 1.2 To determine the number of individuals who can perform a home test with the DNA1 kit with sufficient blood for analysis.
- 1.3 To correlate COPD severity scores with specific SERPINA1 variants.

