3. STUDY OBJECTIVES

3.1 Primary Aim:

The number of individuals with additional *SERPINA1* mutations in the PiMZ COPD cohort will be compared to the number of individuals with additional *SERPINA1* mutations in the PiMZ cohort without COPD.

The primary analysis will determine whether *SERPINA1* genetic signatures detected by sequencing correlate with presence of COPD in PiMZ individuals.

3.2 Secondary Aims:

- 3.2.1 To determine the number of individuals who can perform a home test with the DNA1 kit with sufficient blood for analysis. Among people who desire to test, the portion of people able to successfully obtain a sufficient sample in the home setting using a DNA1 test kit will be determined.
- 3.2.2 To correlate COPD severity scores to specific SERPINA1 variants.
- 3.3 To invite participation in the MUSC Alpha-1 Biorepository Participants will be invited to donate to the MUSC Alpha-1 biorepository by submitting samples in provided PAXgene DNA, PAXgene RNA and EDTA plasma tubes. Copies of spirometry will be requested and COPD questionnaire data linked. These biosamples will be linked to the sequence data for longitudinal transcriptional and proteomic data. Biologic samples are stored for future use with permission for study of Alpha-1, genomics and epigenetic factors. A separate informed consent for biorepository participation will be provided to interested individuals (Pro00039387).

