4.2 Invited participants

Participants tested through the ACT study have already been genotyped, AAT level tested, and reported presence or absence of COPD and demographic information. Classic homozygous AATD has been ruled out. Additionally, these individuals have consented to be contacted for possible participation in Alpha-1 and/or genetic testing-related studies. The MZ cohort with the lower quartile of AAT level is selected as the most reasonable first population for a study of this nature that seeks to identify whether previously untested *SERPINA1* variations correlate with COPD. MZ individuals in the lower quartile of level report the highest MZ incidence of COPD, and this cohort of MZs contains sufficient numbers to obtain matched pairs of COPD-affected and control individuals from this target group. Based on findings of this pilot study, studies of this nature may be expanded to include matched pairs from other MZ-level cohorts and other COPD populations in the future. The 25% of the MZ cohort with lowest levels will have A1-PI values from 11 to approximately 16 uM with the median MZ value equal 19.6 uM.

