5. STUDY DESIGN AND PROCEDURES

5.1 Overview

The MZ Alpha-1 Carrier Genomics study is a pilot study that will enroll up to 150 MZ individuals, with a goal of attaining 50 matched pairs. COPD+ and COPD- individuals will be matched on age, sex, race and smoking history. Any consented individuals who do not have a match in the study cohort will be allowed to continue with participation. Their samples will be analyzed as unmatched COPD + or – samples, which will be accounted for statistically and discussed in study reports.

Presence and severity of COPD is assessed by a COPD severity score for each registrant in the ACT database. We will additionally ask as part of this study that current COPD questionnaires and demographic surveys be completed, and that patients submit previous lung function testing if this has been done. Participants will be mailed a DNA1 test kit to obtain and return a blood sample by finger stick for the purpose of *SERPINA1* gene sequencing. Gene sequencing at Biocerna LLC will identify, if present, genomic signatures that may correlate with COPD in this cohort. Biocerna LLC will determine likely pathogenicity of sequence variants detected blinded to knowing COPD-status of the patient tested. Statistical analysis will correlate genetic findings with COPD presence and severity. Participants will receive their results by mail. Participants will also be invited to contribute additional samples to the MUSC Alpha-1 Biorepository.

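### The 1:1 paired primary test cannot use sequenced participants who have no partner; variable-ratio matched sets would recover part of that information at almost no cost.

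*Protocol*

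**What the plan says.** **Primary test.** Protocol 6.1 and SAP item 1 compare the number of likely significant mutations between COPD participants and matched controls with a paired t-test. Protocol 5.6 step 8 rests the study's conclusions on it: "Statistical analysis of all matched pairs using paired T-test and descriptive analysis will allow for conclusions of this pilot study to be made".

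**People without a partner.** They stay in the study and are sequenced (5.1). Step 8 adds that "Participants for whom no match is available in the study cohort will be included in an uneven COPD"-positive/negative arm analysis and aggregate reporting. Protocol 5.1 and 6.2 and the SAP promise that unmatched participants or uneven arms will be accounted for, without naming a model or an adjustment.

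**Numbers.** Protocol 6.2 and the SAP aim for 50 pairs, or 100 samples, from up to 150 enrolled. One allowance covers both unreturned kits and failure to match.

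**Matching factors.** There are three lists:
- Section 1: "compared to age, race, sex, AAT level and smoking status matched individuals who do not have COPD in the PiMZ ACT cohort"
- Section 5.1: "COPD+ and COPD- individuals will be matched on age, sex, race and smoking history"
- Section 5.6 step 4: "MUSC will perform matching of age, sex, and smoking-status COPD-affected and control MZ participants"

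No age band or caliper is given.

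**Recruitment.** More than 370 people are to be invited (5.2). Section 4.2 says the cohort is large enough to supply matched pairs, without figures, and that ACT participants "have already been genotyped, AAT level tested, and reported presence or absence of COPD and demographic information". Step 1 of 5.6 adds: "Follow-up calls may be made to boost initial recruitment and matching".

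**The concern.** A paired t-test works on within-pair differences, so a person without a partner contributes nothing to it. The plan expects such people, sequences them, and then sends them to an analysis with no stated method and no link to the primary test. A pilot with a fixed supply of 150 kits has reason to use each returned sample in its main comparison. A set with one case and two or three controls (or the reverse) keeps the matching and uses some of the people that 1:1 pairing leaves out.

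The matching rule itself is unsettled. Race and AAT level come and go between the three lists, and the age tolerance is open, so the number of pairs cannot be forecast from the documents.

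**Working it through.** **1. The plan's own figures.** 50 pairs × 2 = 100 samples, which is consistent. 100 of 150 implies a return rate of 100/150 = 66.7%. No COPD share, match rate, effect size or power is stated, so there is no further figure to reproduce.

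**2. When nobody is left out.** 100 samples give 50 pairs only if exactly 50 have COPD and everyone has a partner. Even with perfect matching, the binomial chance of exactly 50 of 100 is 8% at a true COPD share of 50%, and 1% at 40%.

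**3. Information per set.** With equal variances, a set of one case and r controls (or the reverse) has information proportional to r/(1+r): 1/2 for a pair, 2/3 for 1:2, 3/4 for 1:3. Examples with 100 samples, everyone matchable:
- 50/50: 50 pairs, 50 × 1/2 = 25. Sets add nothing.
- 40/60: 40 pairs give 20. Sets (20 of 1:2, 20 of 1:1) give 13.33 + 10 = 23.33, ratio 1.17.
- 30/70: 30 pairs give 15. Sets (10 of 1:3, 20 of 1:2) give 7.5 + 13.33 = 20.83, ratio 1.39.

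**4. Matching within cells.** Simulation, 1,500 runs per case. All settings are assumptions: 16 cells (sex × smoking × four 10-year age bands), race not matched, sex 50/50. *Same profile*: both arms 50% smokers, ages spread evenly. *Different profile*: COPD+ 70% smokers, age bands 10/20/30/40%; COPD- 40% smokers, age bands 30/30/25/15%. Sets are capped at 1:3 in either direction.

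| Returns | Profile | COPD share | Mean pairs | Samples in pairs | Samples in sets | Information, sets/pairs |
|---|---|---|---|---|---|---|
| 100 | same | 50% | 34.3 | 68.6 | 91.8 | 1.20 |
| 100 | same | 40% | 32.6 | 65.2 | 89.4 | 1.22 |
| 100 | same | 30% | 27.2 | 54.4 | 80.1 | 1.27 |
| 100 | different | 50% | 26.2 | 52.4 | 76.6 | 1.26 |
| 100 | different | 40% | 25.3 | 50.6 | 74.1 | 1.26 |
| 100 | different | 30% | 22.2 | 44.4 | 66.2 | 1.27 |

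At 150 returns the same cases give 35 to 56 pairs, a ratio of 1.18 to 1.28, and a chance of reaching 50 pairs from 0 to 95%. A gain appears even at a 50% COPD share because individual cells are unbalanced.

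**5. Illustration in power.** Assume 100 returns, 40% COPD, the same cells, carriers 25% vs 5%, and 15% of carriers with a second mutation. The paired t-test on the count has power 57.9% (same profile) or 46.5% (different profile). An exact within-set test on the same count has 68.6% or 58.3%. The gains are 10.7 and 11.8 points. The carrier rates are assumed, so only the direction and rough size should be read from this.

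**6. Ordering invitations.** Enrolment stops at 150. If fewer than 150 of the 370 accept, all who accept are enrolled and order is irrelevant. The threshold is 150/370 = 40.5%, slightly lower if the pool is larger. Simulated gain from ordering by COPD status and matching stratum, with two-thirds of kits returned: about 0 to 1 pair at 30-40% take-up, and about 5 to 15 pairs at 50-70%. These are upper limits, because the simulation knows who is willing and a caller finds out only by calling.

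**The case against.** A 1:1 paired comparison is a valid and coherent design, and the study is a pilot that openly has no power analysis. Match availability was considered: section 4.2 asserts that numbers suffice, and step 1 of 5.6 already allows calls to improve matching. If 100 samples do form 50 pairs, matched sets change nothing. Every input that drives the size of the gain is assumed. All of this stands, and it limits the point to an efficiency improvement.

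Three stronger readings are tempting, and the documents do not support them.
- *Unmatched data are thrown away.* They are not. These people enter the uneven-arm analysis and aggregate reporting, and the severity analyses in 6.1.1 and SAP item 2 are not restricted to pairs. The loss is from the primary test.
- *The plan will miss 50 pairs, or is underpowered.* No power is claimed, 100 returns is a minimum, and at 150 returns the chance of 50 pairs depends almost wholly on the assumptions.
- *Ordering invitations will raise the pair count.* It does so only above the take-up threshold, and take-up is not given.

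The objection leaves three things unanswered: the assurance in 4.2 carries no figures, the uneven-arm analysis has no method, and the lists of matching factors disagree.

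**Conclusion.** The point holds as a cheap improvement. Under the stated assumptions (30-50% COPD, matching on sex, smoking and 10-year age bands), 31 to 56 of 100 returned samples fall outside the primary test. Matched sets bring back roughly 20 to 30% more information than the pairs hold. The gain shrinks as the cells become better balanced and vanishes when every sample is paired. Sets do not recover everyone: in the simulation 8 to 34 of 100 samples still belong to no set.

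The gain does not depend on changing the outcome. Section 3.1 counts individuals ("mutations in the PiMZ COPD cohort will be compared to the number of individuals with additional" mutations in the cohort without COPD), while 6.1 counts mutations. That mismatch is a separate matter, and a within-set test exists for either outcome.

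**What to change.** (a) Reconcile the matching factors in sections 1, 5.1 and 5.6 step 4, and fix the age band or caliper.

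(b) In 6.1, 5.6 step 8 and the SAP, state that matched sets (1:1 up to 1:3 in either direction) are formed before sequence results are linked to COPD status. Make the primary test a within-set analysis of whichever outcome the plan settles on: an exact permutation test for the mutation count, or exact conditional logistic regression for carrier status, which fits the aim in 3.1.

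(c) Make the uneven-arm analysis a named sensitivity analysis on all sequenced participants, adjusted for the matching factors, for example by Firth logistic regression.

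(d) Optionally, order invitations and the follow-up calls of 5.6 step 1 by COPD status and matching stratum, using data ACT already holds. State that this helps only if take-up among the 370+ exceeds about 40.5%.

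**Cost.** Changes of wording, slightly more coding and, if (d) is adopted, a different calling order. No extra participants or kits are needed. Participants who fit no set would, for the COPD comparison, still enter only the sensitivity analysis.

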5.7.1 Blood Samples

Safety and Processing: Samples will be received by the CLIA certified Biocerna Laboratory in Gaithersburg, MD where safety and sample processing will occur per their usual protocols. Biocerna runs the DNA1 analysis on a clinical and commercial basis and has necessary and proper protocols in place to receive and handle specimens of this study.

5.7.2 Sequencing/ Integrated Genomics

Genetic sequencing is used to determine the order of nucleotides within a gene. State of the art next generation sequencing methods will be applied to detect sequence variants in all regions of the *SERPINA1* gene, including regions upstream and downstream of coding regions of the gene, promoters and regulatory regions. Such testing is more thorough than that which is traditionally performed on a clinical basis yet the role of various mutations within and around the SERPINA1 coding region is potentially important in pathogenicity. Genomic interpretation software and models will be used by Biocerna to assign likely pathogenicity of genomic findings blinded to knowing whether the individual who provided the sample has COPD.

5.8 Questionnaires

St. George's Respiratory Questionnaire (SGRQ)

This biomarker for COPD quantifies a patient reported outcome.

Repeat COPD Severity Score

This assesses clinical severity of COPD. Interval assessment allows for disease progression to be inferred.

Demographic questions not already in ACT

Demographic questions to ensure fidelity of matching will be asked. See corresponding questionnaire.

5.9 Ethical Considerations

5.9.1 Human Subjects' Protections and Risk

DNA1 test kit finger stick

Finger stick is a common method to obtain blood spots for testing. Blood obtained by finger stick involves puncture of the skin with a needle that can cause pain. Very rarely, infections can occur at the site of puncture. Proper safety instructions including proper disinfection of the puncture site prior to needle stick are provided with each test kit. The aforementioned risks are described in the informed consent.

Genetic Testing

SERPINA1 genetic testing risks include the possibility of identifying previously unknown genetic risk for COPD or identifying a genetic change for which the significance is unknown. Testing and results of testing may be associated with feelings of anxiety and uncertainty. Because genetic variants are often shared by family members, testing may inadvertently reveal risk to relatives. The aforementioned risks, as well as potential benefits of knowing genetic information, are described in the informed consent. Study personnel are available to answer questions participants may have prior to or during participation. The Alpha-1 Foundation, under direction of PI [name] and co-investigator [name], offers free genetic counseling services for Alpha-1. Genetic counseling may help people understand medical and familial implications of SERPINA1 results and assist in psychosocial adaptation. The phone number for free genetic counseling service is provided on all results.

Confidentiality

There is a risk to confidentiality. Source data will be kept electronically under password protected systems. Questionnaires or paper documents will be kept in secure areas. Data transmission will be encrypted with a 128-bit VPN approach. Biocerna and MUSC systems are designed to be HIPAA compliant. Collection of DNA and RNA can lead to identification of patients although there is no attempt to do so in this project. Any loss of confidentiality from any participant will be reported to the IRB.

All study personnel are certified in the ethical conduct of human biomedical and genetics research and HIPAA information security. Proof of training will be collected from all study personnel.

Longer descriptions of human subjects protections are provided in the informed consent.

